18 POTENTIAL BENEFITS

The pivotal trial cohort of subjects being followed in this study demonstrated a powerful, robust result at Month 3 with the ExAblate group experiencing a highly significant improvement in the PE and all secondary confirmatory endpoints (See table). The outcomes were essentially unchanged and still favorable by Month 12.

| Efficacy Analysis Summary | | | | | |
|---|--------------------------------------|------------------|------------------------------|---------------------------------------|---------------------------|
| | % of Improvement At Month-3 – ITT | | | % of Improvement At Month 12 – ITT | |
| | ExAblate (N=56) | Sham (N=20) | Between Groups p-value | ExAblate (N=56) | P-value Vs Baseline |
| Primary Endpoint – Composite Tremor/Motor Function | 46.9% | - 0.1% | p< 0.001 | 39.6% | p< 0.001 |
| ..Lower 95% CI | 40.3% | -9.6% | | 34.0% | |
| Upper 95% CI | 53.5% | 9.5% | | 45.3% | |
| CRST, Part A- Tremor “Posture” | 64.3% | - 4.4% (n=17) | P<0.001 | 65.5 % | p< 0.001 |
| ..Lower 95% CI | 52.1% | -26.9 | | 54.7 % | |
| Upper 95% CI | 76.5% | 18.2 | | 76.3 % | |
| CRST, Part C | 63.8% | 1.8% | p< 0.001 | 64.0% | p< 0.001 |
| ..Lower 95% CI | 55.3% | -6.7% | | 55.2% | |
| Upper 95% CI | 72.4% | 11.1% | | 72.7% | |
| QUEST | 43.2% | 5.0% (n=19) | p< 0.001 | 47.1% | p< 0.001 |
| ..Lower 95% CI | 34.3% | -14.9% | | 36.5% | |
| Upper 95% CI | 56.3% | 36.2% | | 62.1% | |

A negative sign “-“ indicates worsening

The safety profile for the pivotal trial cohort demonstrated a rather benign and favorable profile in relation to benefit. Many events were considered Transient and Unrelated and most resolved. The remaining events were Procedure or Thalamotomy related events. All but one were Mild / Moderate in severity. Only 1 serious, related event occurred of Moderate Numbness/Tingling of the thumb which interfered with the subject's ability to hold a pen and write at work.

This PAS is simply an observational study to collect longer-term safety and durability of treatment effect in the IDE study population all the way out to 5 years.

19 MONITORING PLAN

Clinical Monitoring for this study will be managed by InSightec. The Clinical Monitor is qualified by training and experience to oversee the conduct of this study. The Clinical Monitor's responsibilities include maintaining regular contact with each investigational site through telephone contact and on-site visits, to ensure that:

- The trial is conducted according to FDA and GCP requirements;
- The trial is conducted according to InSightec internal SOPs
- The Investigational Plan is followed;
- Complete, timely, and accurate data are submitted;
- Problems with inconsistent or incomplete data are addressed;
- Complications and unanticipated adverse effects are reported to the Sponsor and the IRB;
- The site facilities will be monitored to stay adequate to meet the requirements of the study.

Sites should make every effort to contact all subjects for study follow-up to encourage visit compliance. Sites should keep a log of dates of attempted contact and results. After 3 unsuccessful attempts at contact (e.g., by telephone or email) and sending 1 certified letter to solicit their visit compliance a subject may be considered lost to follow-up.

The Clinical Monitor will continue to perform on-site monitoring visits as frequently as deemed necessary. At this visit and all monitoring visits, the Clinical Monitor will compare the data entered onto the CRFs with the hospital or clinical records (source documents). Source documentation must be available to substantiate adherence to protocol procedures, adequate reporting and follow-up of AEs, and verification of all clinical data captured at the visit. Findings from the review of CRFs and source documents during a monitoring visit will be discussed with the PI. Completed paper or electronic CRFs will be reviewed prior to data closure. The dates of the monitoring visits will be recorded in a Log to be kept at the clinical site. During monitoring visits, the Sponsor expects that the study coordinator and the PI will be available, the source documentation will be available, and a suitable environment will be provided for review of Study related documents.

Monitoring procedures will follow the Sponsor SOPs.

19.1 Electronic Data Capture (EDC)

Electronic CRFs (eCRFs) will be to capture protocol-specific information during the conduct of this study. This electronic data capture of the eCRFs is based on the Oracle Software system, and is designed, run and hosted by Sponsor (Haifa, Israel).

20 INVESTIGATOR RESPONSIBILITIES

The Principal Investigator will be required to sign the Investigator Agreement. All investigators will undergo extensive training on the protocol and operation of the ExAblate system, and provide documentation of their specialized training.

PP	Per Protocol
QUEST	Quality of Life in Essential Tremor
SAE	Serious Adverse Events
SAP	Statistical Analysis Plan
SF	Screen Failure

1 Introduction

The current document describes a full statistical analysis plan (SAP) for the ET-002 Study. ET-002 is a prospective, multi-center, randomized, double-blind (to subjects and Tremor Core Lab assessor), two-arm study. The design of this study includes two stages: Main and Crossover. In the Main stage subjects are randomized in a 3:1 ratio to either ExAblate or Sham Control (henceforth "ExAblate" and "Sham," respectively). The Crossover stage of the study is designed for subjects randomized to the Sham group in the Main stage to receive an unblinded ExAblate treatment, if eligible, at 3-months follow-up post Sham treatment, and to be followed in a similar fashion as the Main stage of ExAblate subjects in terms of planned follow-up visits and assessments.

2 Study Objectives

The objectives of this trial are to evaluate the efficacy and safety of ExAblate system in treatment of medication-refractory tremor in subjects with essential tremor.

The Main stage of the study relates to subjects randomized to either ExAblate or Sham, while the Crossover stage of the study examines outcomes for subjects randomized to Sham who eventually received active treatment with ExAblate. Both Main and Crossover stages of the study provide information on the safety and efficacy of the procedure up to twelve months post-treatment. However, only the Main stage will be used to test device safety and efficacy for the purpose of regulatory approval. The Crossover stage will serve to follow-up safety and efficacy to 12 months.

3 Treatment Groups

Each subject in the Main stage of the study will be randomly assigned to either of the following treatment groups:

- ExAblate – Active treatment with ExAblate
- Sham – Sham Control treatment

The randomization scheme will be 3:1 ExAblate-to-Sham.

Subjects in the Crossover stage of the study will undergo active treatment with ExAblate following their initial Sham treatment.

4 Study Schedule

The following table summarizes the sequence of procedures that a subject in this study will follow.

Summary of Study Schedules and Measurements									
	Screening	Baseline Assessment	Treatment	1 Day	1 Week	1 Month	3 Month	6 Month	12 Month
Consent	X								
Eligibility Evaluation with Labs	X	X							
Medications	X	X	X	X	X	X	X	X	X
30 Day Medication Stabilization		X							
Medical History	X								
Physical Exam	X			X	X	X	X	X	X
Neurological Status	X		X	X	X	X	X	X	X
CRST (Unblinded Site Assessor)	X							X	X
CRST (Blinded Site Assessor)		X				X	X		
CRST (Blinded Tremor Core Lab)		X				X	X	X	X
QUEST	X	X				X	X	X	X
PHQ-9	X					X	X	X	X
CT		X							
MRI		X							X
Treatment			X						
Adverse Events			X	X	X	X	X	X	X
Exit Form									X

5 Analysis Populations

5.1 Safety Analysis Population

The Safety analysis population will include all randomized subjects who received at least one sonication – ExAblate or Sham – in the Main stage of the study, as indicated by the following:

- CRF field "Number of Performed Sonifications" on the ExAblate Treatment Form has a value of at least one
or
- At least one CRF field “Sonication Duration [sec]” on Sonication Form has a value greater than zero.

5.2 Efficacy Analysis Populations

5.2.1 Intent to Treat (ITT)

The ITT analysis population will include all Safety subjects for whom there exist valid baseline measurement and at least one post-baseline measurement on the primary efficacy data.

5.2.2 Per Protocol (PP)

The PP analysis population will include all ITT subjects who have observed primary efficacy data at three months and have no major protocol violations likely to affect outcome.

5.3 Crossover Analysis Population

The Crossover analysis population will include all subjects who received at least one sonication in the Crossover stage of the study.

6 Definition of Endpoints

6.1 Safety Endpoints

The safety endpoints are:

- Adverse Events (AE's)
- Serious Adverse Events (SAE's)

6.2 Efficacy Endpoints

6.2.1 Confirmatory Primary Endpoint

The confirmatory primary efficacy endpoint in this study is Percent Improvement from Baseline at three months post-treatment in the treated (contralateral) upper extremity CRST sub score. For each subject the primary endpoint will be calculated as follows:

1. Identify which side of the brain was treated, as indicated by CRF field “Side of Brain being treated” on the ExAblate Treatment Form
2. If the RIGHT side of brain was treated, then the Tremor Core LAB variables from the LEFT side of the CRST assessment (contralateral side) will be used:

- Part A = item #6 (LUE tremor): Rest + Posture + Action/Intention

Note:

- ➔ If only two individual rates are obtained, the sum will be calculated over the two available rates.
- ➔ If a single individual rate is obtained, Part A will be considered as missing and should be imputed as described in Section 7.1.

- Part B = item #11 Left* + item #12 Left + item #13 Left + item #14 Left + item #15 Left

*Item #11 will be taken into account only for left-handed subjects. For right-handed subjects Part B will be the sum of 4 items only, without item #11.

Note:

- ➔ If a single item is missing, the sum will be calculated over the available items – four items for left-handed subjects and three items for right-handed subjects.

- ➔ If more than one item is missing, Part B will be considered as missing and should be imputed as described in Section 7.1.

3. If the LEFT side of brain was treated, then the Tremor Core LAB variables from the RIGHT side of the CRST assessment (contralateral side) will be used:

- Part A = item #5 (RUE tremor): Rest + Posture + Action/Intention

Note:

- ➔ If only two individual rates are obtained, the sum will be calculated over the two available rates.
- ➔ If a single individual rate is obtained, Part A will be considered as missing and should be imputed as described in Section 7.1.

- Part B = item #11 Right* + item #12 Right + item #13 Right + item #14 Right + item #15 Right

*Item #11 will be taken into account only for right-handed subjects. For left-handed subjects Part B will be the sum of 4 items only, without item #11.

Note:

- ➔ If a single item is missing, the sum will be calculated over the available items – four items for right-handed subjects and three items for left-handed subjects.
- ➔ If more than one item is missing, Part B will be considered as missing and should be imputed as described in Section 7.1.

4. Denote the treated (contralateral) upper extremity CRST sub score at visit [k] as CRST_[contralateral, k], then:

$$\text{CRST}_{[\text{contralateral, k}]} = \frac{\text{Part A} + \text{Part B}}{\text{Total}}$$

Where, *Total* is the maximal sum that could be achieved in Part A and Part B, based on the available items (obtained and imputed). Note that Total should be re-adjusted for each patient based on his/her available information.

For example, if the following conditions for a subject hold

- The treated side of the body is ipsilateral to handedness,
- One item in Part A is missing
- All five items in Part B are obtained

then the Total = 8 (Maximum that could be achieved in Part A) + 20 (Maximum that could be achieved in Part B) = 28

Note: Lower CRST_[contralateral, k] scores are better than higher scores.

5. The confirmatory primary efficacy endpoint (denoted as PE) – Percent Improvement from Baseline at three months post-treatment in the treated (contralateral) upper extremity CRST sub score – will be calculated as follows:

$$PE = \frac{CRST_{[contralateral, Baseline]} - CRST_{[contralateral, 3\ months\ FU]}}{CRST_{[contralateral, Baseline]}} \times 100$$

Note: higher PE values represent improvement.

For both stages (Main and Crossover) the primary efficacy endpoint will be calculated using Baseline score, measured before Main stage treatment initiation.

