6.2.2 Confirmatory Secondary Endpoints

The confirmatory secondary efficacy endpoints in this study are the following:

- SE1=Improvement from Baseline at three months in Quality of Life in Essential Tremor (QUEST). SE1 will be calculated as follows:
 - Categorize the 30 questions into 5 dimensions as follows:
 - Communication: #1 – #3
 - Work and Finances: #4 – #9
 - Hobbies and Leisure: #10 – #12
 - Physical: #13 – #21
 - Psychosocial: #22 – #30
 - Score all applicable questionnaire answers as follows:
 - Never = 0
 - Rarely = 1
 - Sometimes = 2
 - Frequently = 3
 - Always = 4

Note:

- ✓ All questions answered “N/A” will be excluded from the calculation (only questions 4, 5, 7, 8 and 14 can be answered “N/A”)

- ✓ Questions 6, 7, 11 and 12 can only be scored at two values – either a 0 or a 4
- For each subject, calculate dimension score as a percentage of total possible score for each dimension separately. Denote dimension score for dimension [i] at visit [k] as $DS_{[i,k]}$, then:

$$DS_{[i,k]} = \frac{\text{Total applicable points}_{[i,k]}}{\text{Total possible points} (\# \text{ of applicable questions} \times 4)_{[i,k]}} \times 100$$

Note: missing data should be imputed as described in Section 7.2.1.

- For each subject, calculate QUEST summary of dimensions total score as a mean of the five dimension scores. Denote QUEST summary of dimensions total score at visit [k] as $QUEST_{[k]}$, then:

$$QUEST_{[k]} = \frac{\sum_{i=1}^5 DS_{[i,k]}}{5}$$

Note: lower QUEST_[k] scores are better than higher scores.

- For each subject, calculate SE1 as follows:

$$SE1 = \frac{QUEST_{[\text{Baseline}]} - QUEST_{[3 \text{ months FU}]}}{QUEST_{[\text{Baseline}]}}$$

Note: higher SE1 values represent improvement.

- SE2=Percent Improvement from Baseline at twelve months post-treatment in the treated (contralateral) upper extremity CRST sub score. SE2 will be calculated similarly to PE from the previous section, based on 12 months FU data.
- SE3=Percent Improvement from Baseline at three months post-treatment in functional disabilities CRST total score, as measured by CRST Part C. Note, that Part C is performed by Site Assessor only. SE3 will be calculated for each subject as follows:
 - Denote functional disabilities CRST Part C total score at visit [k] as $CRST_C_{[k]}$, then:

CRST_C_[k] = average of answers to items #16-#23 at visit [k]

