Note: if no more than two items are missing, the average will be calculated over the available items; otherwise, CRST Part C total score will be considered missing and should be imputed as described in Section 7.2.3.

- Calculate SE3 as follows:

$$SE3 = \frac{CRST_C_{[Baseline]} - CRST_C_{[3 \text{ months FU}]}}{CRST_C_{[Baseline]}} \times 100$$

Note: higher SE3 values represent improvement.

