7.1 Imputation of Confirmatory Primary Efficacy Data

Confirmatory primary efficacy endpoint (PE) is considered missing if either Part A or Part B at 3 Months FU is missing.

Imputation of Part A

Part A is considered missing if at least two out of the three individual rates within item #5 (or #6) are missing. Missing rates at 3 Months FU will be imputed using LOCF method, i.e. rates from 1 Month FU will be carried forward. If a single individual rate is obtained and two other rates are missing, the non-missing rate will be taken as is and will not be imputed.

Imputation of Part B

Part B is considered missing if more than one required items is missing. Missing items at 3 Months FU will be imputed using LOCF method, i.e. items from 1 Month FU will be carried forward. The obtained items will be taken as is and will not be imputed.

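### The CRST sub score uses whichever items are available at each visit, so Baseline and Month 3 can rest on different items; a minor gap in the primary endpoint that is cheap to close

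*SAP*

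**What the plan says.** SAP 6.2.1 defines the sub score separately for each visit, as Part A plus Part B over Total, where Total is the maximum attainable on the items in hand: "Note that Total should be re-adjusted for each patient based on his/her available information". PE is the percent fall in this score from Baseline to Month 3.

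Small gaps are tolerated without imputation. For Part A: "If only two individual rates are obtained, the sum will be calculated over the two available rates". For Part B: "If a single item is missing, the sum will be calculated over the available items". Carry-forward in SAP 7.1 starts only with larger gaps: "Part A is considered missing if at least two out of the three individual rates within item #5 (or #6) are missing", and Part B needs more than one missing item. The endpoint as a whole then counts as missing only in these cases: "Confirmatory primary efficacy endpoint (PE) is considered missing if either Part A or Part B at 3 Months FU is missing".

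In SAP 6.2.2 the 12-month secondary endpoint follows the same scoring: "SE2 will be calculated similarly to PE from the previous section, based on 12 months FU data". The Part C endpoint (SE3) is an average over eight items with a similar tolerance: "if no more than two items are missing, the average will be calculated over the available items".

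**The concern.** Leaving an item out and shrinking Total treats that item as if it equalled the patient's average on the others. When the same item is absent at both visits this does little harm. When it is absent at one visit only, PE compares two different sets of items, and part of the recorded change is a change of items.

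The rest-tremor rate is the obvious candidate for an item far from the average. Protocol 3.1.1 (criterion 8) requires a postural or intention score of at least 2 in the dominant hand. Protocol 3.1.2 (criterion 19) admits patients with mild resting tremor, and no criterion requires any. A Rest score of 0 is therefore plausible, although no document reports how Rest scores are distributed.

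No planned analysis repairs such a score. The reduced-item PE counts as observed, whereas the SAP 10.6.6 analyses replace missing PE values, and only if much is missing. The stake is a confirmatory endpoint that can show worsening or improvement where there was none.

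**Working it through.** **1. The SAP's own figure.** Each item has a maximum of 4. The SAP 6.2.1 example (one Part A item missing, five Part B items) gives 2×4 + 5×4 = 28, as stated. The full Total is 3×4 + 5×4 = 32 when item 11 counts, and 3×4 + 4×4 = 28 when it does not.

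**2. Unchanged patient, zero-scored item(s) missing at one visit.** The sum is the same at both visits, so PE depends only on the two Totals: PE = 1 - (Total at Baseline)/(Total at Month 3).

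| Case | Missing at Month 3 | Missing at Baseline |
|---|---|---|
| One item, full Total 32 | 1 - 32/28 = -14.3% | 1 - 28/32 = +12.5% |
| One item, full Total 28 | 1 - 28/24 = -16.7% | 1 - 24/28 = +14.3% |
| One Part A and one Part B item, full Total 32 | 1 - 32/24 = -33.3% | 1 - 24/32 = +25.0% |
| One Part A and one Part B item, full Total 28 | 1 - 28/20 = -40.0% | 1 - 20/28 = +28.6% |
| SE3, one of eight items | 1 - 8/7 = -14.3% | 1 - 7/8 = +12.5% |
| SE3, two of eight items | 1 - 8/6 = -33.3% | 1 - 6/8 = +25.0% |

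Scored on common items, every case gives 0.0%.

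**3. Items that are not zero.** For an unchanged patient with sum S out of T, and an item scored x missing at Month 3, PE = 1 - T(S - x)/(S(T - 4)). With S = 20 and T = 32, x = 0, 1, 2, 3, 4 gives -14.3, -8.6, -2.9, +2.9 and +8.6%.

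**4. Arm level.** A zero-scored item missing at Month 3 shifts PE by -14.3 points times the true ratio of Month 3 to Baseline score. The long-term follow-up protocol (Section 18) reports mean PE of 46.9% (ExAblate, n=56) and -0.1% (Sham, n=20), so the ratios are about 0.531 and 1. The shifts are -7.6 and -14.3 points, a gap of 6.7 in favour of ExAblate. At an assumed 5, 10 or 20% of patients affected in both arms, the difference moves by 0.3, 0.7 or 1.3 points. If the item is missing at Baseline instead, the gap is 12.5×(1 - 0.531) = 5.9 points against ExAblate.

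The standard error comes from the same table. The ExAblate interval 40.3 to 53.5 has half-width 6.6; 6.6/2.004×√56 gives SD 24.6. The Sham interval -9.6 to 9.5 has half-width 9.55; 9.55/2.093×√20 gives SD 20.4. Then √(24.6²/56 + 20.4²/20) = 5.6.

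**5. Does common-item scoring help?** Example patient: Baseline Part A (Rest, Posture, Action) 0, 3, 3 and Part B 3, 3, 3, 3, 2; Month 3 Part A 0, 1, 1 and Part B 2, 2, 2, 2, 2. True PE is 1 - 12/20 = 40.0%.
- Rest missing at Month 3: as written 1 - (12/28)/(20/32) = 31.4%; common items 1 - 12/20 = 40.0%.
- Posture missing at Month 3: as written 1 - (11/28)/(20/32) = 37.1%; common items 1 - 11/17 = 35.3%.

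A simulation on assumed inputs gives the same mixed picture. Inputs: rounded 0-4 items; Baseline means Rest 0.44, Posture 2.2, Action 2.7, Part B 2.4-2.6; patient and item SD 0.5; visit noise SD 0.4; ExAblate ratio 0.36 for Posture and 0.53-0.55 otherwise, patient log-SD 0.35; about 199,000 patients per arm. Among affected patients:
- Rest missing at Month 3: mean error falls from about -11 to 0 (Sham) and from about -6 to 0 (ExAblate).
- Random item missing at Month 3: root mean square error falls from 6.1 to 4.6 (Sham) and from 4.5 to 3.9 (ExAblate).
- Posture missing at Baseline, ExAblate: common items are worse, with mean error -2.4 against 0.1 as written.

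**The case against.** Re-adjusting Total by patient could be read as one common Total per patient. The formula does not support that: the score is indexed by visit and its numerator is summed over what that visit supplies. A shared Total would not by itself match the items.

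The rule is also a deliberate convention, with proration for small gaps and carry-forward for large ones. A similar tolerance appears for Part C and for two QUEST dimensions (SAP 7.2.1). That explains the thresholds, but not why the two visits need not share items. It does mean that changing PE, SE2 and SE3 leaves SE1 on its own rule.

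The strongest objection is about size, and it stands. The double-digit figures for a single item need a zero-scored item (or one equally far from the patient's average) missing at exactly one visit. Filming is standardised for the core lab (Protocol 4.1.5, Videotaping Procedure), and nothing suggests that upper-limb Rest is selectively lost. If every item is equally likely to be missing, the mean shift is about zero and only noise is added.

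It also stands that common-item scoring is not better in every case, as step 5 of the working shows.

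**Conclusion.** The gap is real but minor. Followed exactly, the rule can give an unchanged patient -14.3% or +12.5% (full Total 32), or -16.7% or +14.3% (full Total 28), from one zero-scored item missing at one visit. The error is much smaller for items near the patient's average.

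A reader might infer that the Month 3 comparison is unreliable. The documents do not support that. They give no item-missing rate, and a shift of 0.3-1.3 points at assumed rates of 5-20% is small against a standard error of about 5.6 and reported means of 46.9% and -0.1%.

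Two other inferences should also be resisted. The Sham count of 17 of 20 for Posture in the long-term follow-up protocol (Section 18) does not show that items were missing: its cause is not stated, and a zero Baseline Posture score would also leave the percentage undefined. Nor is there clear evidence that a badly incomplete Baseline could enter the analysis. SAP 5.2.1 requires a "valid baseline measurement and at least one post-baseline measurement on the primary efficacy data", and the 6.2.1 thresholds for calling Part A or Part B missing are not limited to one visit, so a natural reading already excludes such patients.

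**What to change.** In SAP 6.2.1, and by reference for SE2, keep the existing thresholds and the existing carry-forward for larger gaps. Then compute Part A, Part B and Total at both Baseline and follow-up only on items available at both visits, whether obtained or imputed under 7.1. Treat SE3 in the same way, with at least six common items. In the per-protocol set, where SAP Section 7 allows no imputation, use the items obtained at both visits.

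Where too few common items remain, keep the current per-visit score so that no new missing PE is created. An example is Rest missing at Baseline and Posture at Month 3 in the per-protocol set, which leaves a single common Part A rate.

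Report the number of reduced-item patients per arm, and rerun PE under the current per-visit rule as a sensitivity analysis whatever the amount of missing data.

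Extending carry-forward to single missing items is not recommended. It assumes stability since Month 1; if Month 1 scores were 20% lower than Month 3 (an assumption), a similar simulation with a random item missing at Month 3 showed it adding about +1.4 points (ExAblate) and +2.5 points (Sham) of bias in affected patients.

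The cost is wording and programming, with no new data. The downside is that an item scored at only one visit is ignored, which sometimes moves PE slightly further from the truth (35.3% against 37.1% in the Posture example, true value 40.0%). The sensitivity analysis would show whether that matters.
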